Effects over time: We will also assess the intervention effects over time using longitudinal data for both suicidal ideation and suicide attempt. For suicidal ideation, we will use a linear mixed-effects model with ideation assessed at baseline, 3 months, and 6 months. The model will allow the full use of all observed data despite missing outcomes at one or two assessment times and will give unbiased estimates as long as the missingness does not depend on the unobserved missing data (missing at random). For suicide attempt, we will use a generalized linear mixed-effects model with logit link for any suicide attempt in the prior 3 months as a binary response variable assessed at 3 and 6 months. These models will include participant as random intercepts to take into account the correlation of data within person over time. The models will allow estimation of the time-averaged effect of the intervention if the response to the intervention is immediate and lasting, or estimate the differential effect of the intervention over time if a significant interaction between time and intervention is found, such as different trends between the study groups. Whether we compare the time-averaged effects or the rates of changes between two groups, we will be guided by careful graphical exploration of the longitudinal data over time between the two groups. For example, if we find decreasing BSI scores from baseline to 3 months in both groups, but with a larger decrease in the intervention group, this will be modeled with interaction terms of time indicators for 3 and 6 months each by intervention group. The coefficients from the interaction terms of the BSI model will then allow testing for the between-arm difference in decrease in BSI from baseline to 3 months and baseline to 6 months. Similarly, the interaction term of the suicide attempt model will allow testing if the odds ratio of suicide attempt associated with the intervention differs from month 3 to month 6.

Secondary Outcomes

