The effects of the intervention on the primary hypothesized mediators of hope (Hope Scale and Beck Hopelessness Scale) and belongingness (NIH Toolbox measures) will be assessed using multiple regression models based on a similar model as described under aim 1 for suicide ideation. Primary interest will be comparisons between treatment arms at 3 months (primary analysis) and 6 months (secondary analysis). Similar exploratory analyses will be used to assess intervention effects at 3 and 6 months on functioning, quality of life, depression, patient activation, healthcare utilization, and medication adherence.

Figure 4. Mediation Model of Intervention Effectiveness

Mediation of Intervention Effects on Suicide Attempts and Suicidal Ideation:
We will examine whether any improvements in the primary outcomes of suicide attempts or suicidal ideation are mediated through improvements in hope and belongingness in

primary exploratory analyses. The role of functioning, quality of life, depression, patient activation, healthcare utilization and medication adherence as mediators will be assessed in secondary exploratory analyses. To test whether a variable might be a mediator, we will first test the associations between the intervention arm and the mediator (described in above bivariate analyses), and then the mediator and the outcome of interest using bivariate analyses (e.g., hope at 3 months and suicidal ideation at 6 month). A variable will be considered a potential mediator if the variable at the 3-month assessment is associated with the intervention arm and with the outcome at 6 months as determined by a significance level of $p < .10$.

Potential mediators (at 3 months) will then be included as covariates in multivariate regression models predicting the primary outcomes at 6 months (Figure 4). If, as hypothesized, the intervention's effects on the primary outcomes are mediated through hope and belongingness (or other exploratory mediators), the variance in the 6-month outcomes explained by the intervention group will be less once the mediator variables are included in the models. Changes from baseline to 3 months will also be examined as potential mediators.

The intervention effects on any and number of readmissions to a psychiatric inpatient unit, emergency department visits, and outpatient mental health treatment visits (e.g., medication prescriber or psychotherapist) will be analyzed using generalized linear models with appropriate link function.

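### In the supplementary longitudinal models, plots of the two arms and an interaction test with no stated level choose the reported contrast, so the result carries no known 5% error rate

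*Combined protocol and SAP*

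**What the plan says.** The Effects over time paragraph (Statistical Analyses Plan, Data Analysis) adds longitudinal models to the primary 6-month regressions. For ideation, "we will use a linear mixed-effects model with ideation assessed at baseline, 3 months, and 6 months". For attempts, a logistic mixed model uses the 3- and 6-month visits only. Two summaries are offered:

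- "The models will allow estimation of the time-averaged effect of the intervention if the response to the intervention is immediate and lasting";
- or the models will "estimate the differential effect of the intervention over time if a significant interaction between time and intervention is found".

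The next sentence says how the choice is made: "Whether we compare the time-averaged effects or the rates of changes between two groups, we will be guided by careful graphical exploration" of the data in the two groups. No level is attached to the word significant, and no criterion defines an immediate and lasting response.

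A worked example follows. If ideation falls in both arms but falls more under the intervention, "this will be modeled with interaction terms of time indicators for 3 and 6 months each by intervention group", and the coefficients will "allow testing for the between-arm difference in decrease in BSI from baseline to 3 months and baseline to 6 months". For attempts, the interaction "will allow testing if the odds ratio of suicide attempt associated with the intervention differs from month 3 to month 6".

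Elsewhere the plan does state levels. Sample Size uses a two-sided 0.05 test. The mediator screen requires a variable to be "associated with the intervention arm and with the outcome at 6 months as determined by a significance level of" p < .10. Neither level is tied to the time-by-arm interaction.

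**The concern.** The plots are drawn by arm, so the analyst would see the treatment difference before deciding which treatment contrast to report. A p-value for a contrast chosen in this way is not the p-value of a contrast fixed in advance.

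For ideation the two branches also overlap. Baseline is a response in the model and is measured before allocation (Randomization and Blinding). An effect that appears by 3 months and persists to 6 months is therefore itself a time-by-arm interaction, so one pattern meets both conditions. The plan also does not say which visits the ideation average covers.

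What is at stake is limited but real. Approach to Missing Data cites the mixed model as the unbiased estimate if data are missing at random, and Sample Size assumes 25% dropout. If this model is to back up the primary result, the reader needs to know which contrast it reports and at what error rate.

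**Working it through.** **1. The plan's own figures.** With 184 per arm, 22% v 36% and two-sided .05, the normal approximation gives 84.4% power (plan: 84%). For d = 0.34, Φ(0.34·√(184/2) − 1.96) = 90.3% (plan: 90%). Both belong to the fixed 6-month analyses. The plan states no error rate or power for the longitudinal models.

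**2. Assumed rule.** The plan has no strict rule, and a choice made by eye has no calculable rate. I therefore took the nearest strict version: test the interaction at .05; if it is not significant, test the time-averaged effect at .05; if it is, apply one of the options below.

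**3. Ideation inputs.** Arm differences at baseline, 3 and 6 months, no true effect, normal approximation. Equal correlation between visits, as a random intercept implies, of 0 to 0.7 (assumed; the documents give none). Data complete, or with 21%/25% missing at 3/6 months (pilot 3-month loss 1 − 49/62 = 21%; planned dropout 25%), or 25%/25%. 1,000,000 null draws per setting.

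| What counts after a significant interaction | Average = arm main effect over three visits | Average = mean of the 3- and 6-month change contrasts |
|---|---|---|
| The interaction itself | 9.7%–9.8% | 7.5%–7.6% |
| A 3- or 6-month change coefficient at .05 | 8.9%–9.1% | 6.6%–6.9% |
| Only the 6-month change coefficient at .05 | 7.2%–7.3% | 5.0%–5.1% |
| Nothing | about 4.8% | about 2.5% |

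Two other readings of the average (post-baseline mean difference, with or without baseline adjustment) fall between the columns. Check on the first column: the main effect and the interaction are independent, so the top cell is 1 − 0.95² = 9.75% and the bottom is 0.95 × 0.05 = 4.75%. The right-hand column is closest to the plan's example, which works with changes from baseline; with a change coefficient counted it gives 5.0%–6.9%. If the interaction were tested at .10, the second row would run from 8.2% to 12.2% across both columns.

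**4. Attempts.** Same rule, two visits, complete data or 21%/25% missing. If the interaction is treated as heterogeneity only, the rate is 0.95 × 0.05 = 4.75%. Otherwise:

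| Correlation between visit effects (assumed) | 6-month odds ratio then tested | Either visit's odds ratio then tested |
|---|---|---|
| 0 | 6.4%–6.5% | 8.0% |
| 0.3 | 6.0% | 7.2% |
| 0.6 | 5.5%–5.6% | 6.3% |

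**5. Fixed alternatives.** One contrast named in advance has a 5.0% rate. Fixing both visits without naming a lead, and counting either at .05, gives 1 − 0.95² = 9.75% at correlation 0, 9.5% at 0.3 and 8.8% at 0.6. That is higher than the rates in step 4, so the fix must name a lead visit.

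**The case against.** The strongest reply is that nothing confirmatory rests here. The Bivariate/Multivariate Analyses paragraph fixes the 6-month regressions as primary and separately promises a 3-month analysis, so fixed comparisons at both visits exist whatever the longitudinal models show. Each coefficient, reported as that coefficient, keeps its nominal level. All of this stands, and it is why the point is minor.

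It can also be said that significant naturally means .05, since the plan writes out p < .10 where it departs from that. This is reasonable, and all the rates from 2.5% to 9.8% already assume it. It does not settle the choice by graph.

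A third reply is that the rates come from rules the plan does not state, and that they run from half to about twice the nominal level. That is correct. They show that the error rate is undetermined, not that it is always inflated.

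A reader might also infer that the time-averaged ideation effect is diluted by the baseline visit. The documents do not support this. It needs an arm main effect averaged over all three visits, which the text never specifies; the worked example uses changes from baseline and is not diluted, and the attempt model has no baseline response.

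**Conclusion.** The point holds as a minor one. The plan states a data-guided choice of contrast, and nothing else in the SAP fixes that contrast. Under the assumed strict rules with the interaction at .05, the null rejection rate for ideation is about 2.5% to 9.8%. For attempts it is about 5.5%–6.5% or 6.3%–8.0%, according to which visit's odds ratio is then tested. These figures rest on a normal approximation, equal correlation between visits and assumed correlation values. The ideation rates barely change with the correlation; the attempt rates fall as it rises.

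It would be wrong to infer that the trial's main type I error is inflated. The primary 6-month regressions, their stated 84% and 90% power and the separate 3-month analysis do not depend on this choice.

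**What to change.** Make the worked example the rule.

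- **Ideation:** one arm-by-time model, with the baseline Beck score either as a covariate or as a response with equal baseline means across arms.
- **Attempts:** one arm-by-visit model.
- **Both outcomes:** name the 6-month contrast as lead, and label the 3-month contrast and the mean of the two as secondary or descriptive.
- Use plots and the interaction test for description only, and delete the sentences that let them choose the contrast.

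The cost is SAP wording; no design, sample-size or data-collection change is needed. The document is dated September 25, 2024 and does not say whether outcome data by arm have been examined. If they have, the amended text should say so, because the contrast could then no longer be called prespecified.

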Based on our pilot study findings and those of other randomized controlled trials of psychosocial interventions that included suicide attempts as a primary outcome (91, 92, 109), we powered the study with the assumption that frequency of suicide attempts at 6 months will be 22% in the intervention arm vs. 36% in the control arm. We will enroll 490 patients in total, and assuming a 25% dropout rate, 368 (184 per group) will provide primary outcome data. The proposed sample size is expected to provide 84% power to detect the desired difference between the two groups based on a two-sided 0.05 level test. The estimate of effect is based on an assumption that the effect of PREVAIL will be similar to that reported in a trial of cognitive behavioral therapy for suicide among suicide attempters (N=120) where the re-attempt rate at 6 months was 25% among intervention recipients vs. 40% for controls. (91) Although there is no prior literature comparing the effects of peer support to psychotherapy on suicide-specific outcomes, two meta-analyses have concluded the effects of peer support on depression are similar to psychotherapy. (49, 51) Our estimate of effect is conservatively less than that found for brief psychodynamic interpersonal therapy, where in one trial (N=119) the self-harm rate at 6 months was 9% in the intervention arm compared to 28% for controls. (92) For the primary outcome of suicidal ideation according to the Beck Scale for Suicidal Ideation at 6 months and measures of hope and belongingness at 3 months (Aim 2), our sample of 368 will provide 90% power to detect a standardized effect size (Cohen's d) of .34. For the mediator analysis, the proposed sample size is expected to provide 80% power to detect a significant mediator assuming that the intervention explains about 2% of the variance of the mediator (corresponding to "small" effect based on Cohen's criteria), and about 7% of the variance of suicide ideation is explained by the mediator adjusting for the intervention effect, or vice versa based on joint significance testing for the mediation effect. (110)

Data Analysis

Baseline Analyses

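### The exploratory mediation rule is not the joint-significance test it is powered on, and neither adjusts for baseline, so a variable with no effect on the outcome can pass as a mediator

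*Combined protocol and SAP*

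**What the plan says.** **Sample Size.** For the mediator analysis, "the proposed sample size is expected to provide 80% power to detect a significant mediator". The inputs are stated as "assuming that the intervention explains about 2% of the variance of the mediator", and "about 7% of the variance of suicide ideation is explained by the mediator adjusting for the intervention effect, or vice versa", with the power computed "based on joint significance testing for the mediation effect". The mediator path in that calculation is therefore adjusted for arm, and for nothing else that is mentioned.

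**Secondary Outcomes, paragraphs on mediation.** The analysis is labelled exploratory. It has two steps.

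1. A screen: "A variable will be considered a potential mediator if the variable at the 3-month assessment is associated with the intervention arm" and with the 6-month outcome, each at p<.10. The mediator-outcome association is tested by bivariate analysis.
2. Variables that pass enter the 6-month outcome models as covariates. Under mediation, the plan says, "the variance in the 6-month outcomes explained by the intervention group will be less once the mediator variables are included in the models". No test, interval, minimum fall or indirect-effect estimate is given.

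The section adds that changes from baseline to 3 months will also be examined as mediators, without a separate decision rule.

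**Baseline terms.** The outcome models under Primary Outcome contain arm, site, gender and prior attempt. Baseline ideation, hope and belongingness enter only if they differ significantly between arms (Baseline Analyses) or are associated with missing follow-up (Approach to Missing Data). Neither provision makes baseline mediator and baseline outcome standing terms in the mediation models.

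**The concern.** The power statement and the analysis describe different procedures, so the 80% is not the power of what the plan says it will do.

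The planned procedure also has two routes to a false positive. First, if the intervention affects both the mediator and ideation, arm alone makes the two correlate, and a bivariate test counts that as evidence. Second, people who are more hopeless at baseline are likely to have more severe ideation at baseline, and both tend to persist. Three-month hope and 6-month ideation can then be correlated without one affecting the other. The last step does little to filter these out: once arm is associated with both the mediator and the outcome, some fall in the variance explained by arm is close to automatic.

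At stake is the trial's statement about how the intervention works. The Study Rationale presents the assessment of potential mediators as an advance of this trial.

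**Working it through.** **Inputs from Sample Size.** "We will enroll 490 patients in total"; "assuming a 25% dropout rate, 368 (184 per group) will provide primary outcome data" (490 × 0.75 = 367.5). Arm explains 2% of the mediator, the mediator 7% of ideation given arm, and the ideation effect is d=.34. No alpha is stated for mediation; 0.05 two-sided per path is assumed.

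**Step 1: the plan's own figure.** Joint power = power(path a) × power(path b), from noncentral F tests with f² = R²/(1−R²) and noncentrality f² × 368.
- Path a: f² = .02/.98, power .780.
- Path b: f² = .07/.93, power .9995.
- Joint: .780 × .9995 = .780. With 2.1% in place of 2%, path a gives 80.0%.

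The stated 80% is thus reproduced within its own word 'about'. It matches joint significance at .05; at .10 the joint power is 86.2%.

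**Step 2: how often the planned rule passes a variable with no effect on ideation.** Model: 184 per arm; baseline mediator and baseline ideation correlated ρ; each follow-up value correlated φ with its own baseline; arm moves the mediator (2%) and ideation (d=.34, in the beneficial direction); no path from mediator to ideation. The values of ρ and φ are assumptions, because the documents give none. The rule is both p<.10, then any fall in variance explained by arm.

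A hand approximation shows where the rates come from.
- Arm-mediator correlation: √.02 = .141.
- Arm-ideation correlation: .17/√(1+.17²) = .168.
- Part of the mediator-ideation correlation induced by arm: .141 × .168 = .024.
- Part from shared baseline severity: φ² × |ρ| × √(1−.141²) × √(1−.168²) = φ² × |ρ| × .976.
- z = (sum of the two parts) × √366. The screen passes with probability P(|Z|>1.645) × .862, where .862 is the power of path a at .10.

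| ρ | φ | Sum of parts | z | Screen, approx. | Full rule, simulated |
|---|---|---|---|---|---|
| 0 | any | .024 | 0.45 | .135 × .862 = 12% | about 11% |
| −0.2 | 0.4 | .031+.024 = .055 | 1.05 | .280 × .862 = 24% | about 24% |
| −0.2 | 0.6 | .070+.024 = .094 | 1.80 | .561 × .862 = 48% | about 50% |
| −0.5 | 0.4 | .078+.024 = .102 | 1.95 | .619 × .862 = 53% | 56% |
| −0.5 | 0.6 | .176+.024 = .199 | 3.81 | .985 × .862 = 85% | 86% |

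At ρ = −0.5 and φ = 0.5 the simulated rate is 77%. The fall in explained variance removes few or none of the variables that passed the screen in these settings.

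**Step 3: conditions under which the rate is lower.** With no direct effect of arm on ideation, the rate at ρ = −0.5 is about 17-36%. If arm does not move the variable, it is about 6% or less.

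**Step 4: would the powered test cure it?** Adjusting path b for arm removes the arm-induced part but leaves φ² × ρ. At ρ = −0.5:
- φ = 0.4: .08 × √365 = 1.53; P(Z > 1.96 − 1.53) = .33; × .780 = 26%.
- φ = 0.6: .18 × √365 = 3.44; P(Z > 1.96 − 3.44) = .93; × .780 = 73%.

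The simulated range is 27-73%. With baseline mediator and baseline ideation added, the rate is about 4-5%. In this model all the shared cause passes through the two measured baselines, so that figure is a best case.

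**The case against.** **The text can be read as describing a pattern, not a decision rule.** Passing the screen earns only the label of potential mediator. The sentence about explained variance says what is expected if mediation holds, not that any fall proves it. The later model contains both arm and mediator, so an arm-adjusted mediator coefficient will be available. All of this is correct. But the plan names no other criterion and does not say that this coefficient is tested, so a reader has only the screen and the fall to go by.

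**Baseline is not ignored.** Changes from baseline are also examined, and the arm-to-mediator models follow the Aim 1 model, so they carry site, gender and prior attempt. This stands for the first path. Change scores have no decision rule of their own and do not replace adjustment for baseline mediator and baseline outcome in the second path.

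**Stronger readings a reader might infer, which the documents do not support:**
- That non-mediators would be declared often in general. The excess depends on arm moving the variable, and it is largest when arm also affects ideation directly.
- That using the powered test would be enough. That test adjusts only for arm, and with no direct effect at ρ = −0.5 it errs at least as often as the planned rule.
- That Aim 2 is compromised. Under Intervention mechanisms, Aim 2 concerns effects on hopelessness and belongingness, and Sample Size powers those 3-month comparisons separately (90% for d=.34).
- That the 80% power is miscalculated. The difference between 78% and 80% is rounding.

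**Conclusion.** The point holds in a limited form. The mediation power refers to one procedure and the analysis section describes another, and neither includes the baseline terms that matter most. Read as the only stated criterion, the planned rule passes a variable with no effect on ideation in about 11% to 86% of trials when arm moves the mediator by 2% of variance and affects ideation directly by d=.34. Where it falls in that range depends on the baseline correlation (0 to −0.5) and on persistence (0.4 to 0.6), both assumed. Some baseline correlation is plausible, since the Background describes hopelessness and poor belongingness as established correlates of suicide risk, but its size is not given.

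The direct-effect condition is relevant because the plan asks whether improvements in the primary outcomes are mediated. Most of the gain comes from baseline adjustment rather than from joint significance itself. For suicide attempts, which use logistic regression, the variance explained by arm is not defined. The analysis is exploratory and the primary conclusions do not depend on it, so this is a cheap improvement.

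**What to change.** State in the mediation paragraphs that mediation is judged by joint significance, each path at two-sided .05:

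- Arm to 3-month mediator, adjusted for baseline mediator and the randomization factors (site, gender, prior attempt).
- Three-month mediator to 6-month outcome, adjusted for arm, baseline mediator, baseline outcome and the randomization factors. Baseline outcome is baseline BSS for ideation and prior attempt for attempts.

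Report the indirect effect with a bootstrap interval. Use p<.10 for screening only, if at all, and drop the fall in explained variance as a criterion. Align the Sample Size sentence with this model.

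The cost is SAP wording and modest programming; the variables are already collected at baseline, 3 and 6 months. Fewer variables will be called mediators. Common causes not captured by the baseline measures remain, and the report should say so.

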We will examine the randomization process to determine if there were any between-group differences at baseline, particularly in variables that are thought to be potentially associated with suicide attempts or ideation. T-tests or chi-square analyses, as appropriate, will be used to test for differences in the following baseline variables between study groups: age, severity of suicidal ideation prior to admission, burdensomeness, hope/hopelessness, and measures of belongingness. When there are significant differences in the distribution of these variables, they will be included as covariates in multivariable analyses. Balance is expected for sex and recent suicide attempt due to randomization by minimization.

Data Verification/Univariate Analyses: We will examine the distribution of all study variables for extreme values, missing data, variances, possible coding errors, skewness and whether or how to categorize skewed data. We will describe means (SD) for the continuous measures and frequencies of dichotomous outcomes by study group for each assessment time for the entire sample and for each of the study sites, separately.

Primary Outcome

Primary analyses will determine the effectiveness of PREVAIL in decreasing the risk of any suicide attempt and in decreasing suicidal ideation at 6 months post-randomization. Primary analytic cohort will be "intent to treat", such that all randomized participants will be included according to their original study arm assignment, regardless of whether they subsequently drop out of participation in the intervention. Secondary analyses will be conducted using a "per protocol" cohort where only participants who complete 6 or more peer encounters will be compared to those assigned to the EUC arm. We will evaluate predictors of compliance by defining 6 or more peer encounters as compliance and will also obtain complier average difference (a.k.a. complier average causal effect) assuming a balanced proportion of compliance between arms. The estimates of the three analytic cohorts (intent to treat, per protocol and compliance average difference) will provide more robust understanding of the effect of PREVAIL. (106)

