Approach to Missing Data

Our initial analyses will only use observed data. When data are missing for items within scales, we will use recommended imputation procedures rather than excluding participants from the analyses. For missing follow-up assessments, we will check if missingness is associated with any baseline variables including sites, and will include any such baseline variables in the models evaluating the intervention effect described above. In addition, as described under Effect Over time, the mixed-effects model is expected to provide an unbiased estimate of the intervention effect if missingness is at random. As a secondary analysis, we will also conduct an analysis that imputes missing data. We will likely have some missing baseline values in addition to missing follow-up assessments. Thus we will conduct multiple imputations based on chained equations (sequential regression multivariate imputation) to impute both baseline and follow-up data and will summarize the data using appropriate combination rules. (107, 108)

REGULATORY, ETHICAL AND STUDY OVERSIGHT CONSIDERATIONS

Informed Consent Process

Patients who appear to meet study inclusion and exclusion criteria based on review of medical records and consultation with the attending psychiatrist will be approached by the research assistant (RA) to describe the study, provide information about the randomization and 3 and 6-month assessments, as well as the risks, benefits, and limitations to confidentiality. Patients who state they are interested will be asked to complete a brief cognitive screener to assess whether they are substantially cognitively impaired and therefore unable to give informed consent. Patients who are not substantially cognitively impaired will complete a pre-screening consent form allowing study staff to administer the Beck Suicide Scale and items 4 and 5 of the Columbia Suicide Scale. Patients who have a score >5 on the Beck Suicide Scale will be eligible to participate and obtain informed consent. During the informed consent process, the study will be described and patients will have ample and repeated opportunities to ask questions.

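### The primary 6-month regressions use observed data only and no 3-month information, although the cohort is declared as all randomized; dropout that follows the 3-month course could bias both primary results

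*Combined protocol and SAP*

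**What the plan says.** All references are to the Statistical Analyses Plan in the combined document, unless stated.

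- **Cohort (Primary Outcome).** The primary analysis is intent to treat: "all randomized participants will be included according to their original study arm assignment".
- **Primary tests (Bivariate/Multivariate Analyses).** A logistic regression for attempts and a multiple regression for ideation, both at 6 months, adjusted for site, gender, prior attempt and any covariates imbalanced at baseline.
- **Data used (Approach to Missing Data).** "Our initial analyses will only use observed data". Baseline variables associated with missing follow-up are added to the models. Then: "As a secondary analysis, we will also conduct an analysis that imputes missing data", by chained equations.
- **Longitudinal models (Effects over time).** Mixed models with participant random intercepts: ideation at baseline, 3 and 6 months; attempts in the preceding 3 months, recorded at months 3 and 6.
- **Expected loss (Sample Size).** "We will enroll 490 patients in total, and assuming a 25% dropout rate, 368 (184 per group) will provide primary outcome data".

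**The concern.** The cohort statement promises everyone randomized, but the regressions that carry the primary tests can include only those with a 6-month outcome. What they can adjust for was measured before randomization. The 3-month visit shows who has attempted suicide again and whose ideation remains high, and the primary tests make no use of it to account for missing 6-month outcomes.

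Dropout after a bad first three months is plausible in this population, and baseline covariates cannot fully stand in for what happened after randomization. If such dropout occurs in both arms, a real difference in attempts shrinks. If it differs by arm, a real difference can be hidden or exaggerated, and a difference can appear where none exists.

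There is also a coding gap. The Outcomes section sets the attempt outcome over 6 months, while the longitudinal model uses 3-month windows. Nothing says whether a participant with an attempt reported at month 3 and no month-6 visit is an event or is missing.

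**Working it through.** **1. The plan's own figures.** Evaluable: 490 × 0.75 = 367.5, stated as 368, so about 122 are missing.

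Attempts, 36% vs 22%, 184 per arm, two-sided 0.05, pooled variance under the null:
- SE0 = √(2 × 0.29 × 0.71 / 184) = 0.0473
- SE1 = √[(0.36 × 0.64 + 0.22 × 0.78) / 184] = 0.0467
- power = Φ[(0.14 − 1.96 × 0.0473) / 0.0467] = 84.4% (stated: 84%)

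Ideation: Φ(0.34 × √(184/2) − 1.96) = Φ(1.30) = 90.3% (stated: 90%).

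Both reproduce. Both take the 368 as representative of the 490.

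**2. Attempts: dropout driven by 3-month status.** Let p be the true 6-month rate, f the share of events occurring by month 3, and a = f × p. With dropout 45% after a 3-month attempt and 18% otherwise, the rate among those seen at month 6 is

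R = [0.55a + 0.82(p − a)] / [0.55a + 0.82(1 − a)].

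The dropout rates are assumptions; the documents give none by 3-month status. For f, the pilot's 24% by 3 months (Preliminary Studies) over the planned average of 29% gives 24/29 = 0.83. That ratio is weak. If the 24% is 12 of the 49 three-month completers, its 95% interval is about 15% to 38%, so f could be near 0.15/0.29 = 0.52. I therefore show 0.83 and 0.50. The calculation takes the month-6 visit to capture the whole 6 months and ignores model covariates.

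Worked case, controls, f = 24/29: a = 0.298; numerator 0.164 + 0.051 = 0.215; denominator 0.164 + 0.576 = 0.740; R = 29.0%. Control dropout is 26%, close to the planned 25%.

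| Dropout pattern | f | Control | PREVAIL | Difference | Power |
|---|---|---|---|---|---|
| 25% regardless of outcome | any | 36.0% | 22.0% | 14.0 | 84% |
| 45%/18% in both arms | 0.83 | 29.0% | 17.0% | 12.0 | 79% |
| 45%/18% in both arms | 0.50 | 32.0% | 19.1% | 12.9 | 83% |
| 45%/18% in controls, flat 25% in PREVAIL | 0.83 | 29.0% | 22.0% | 7.0 | 34% |
| 45%/18% in controls, flat 25% in PREVAIL | 0.50 | 32.0% | 22.0% | 10.0 | 58% |
| 30%/22% in controls, flat 25% in PREVAIL | 0.83 | 34.0% | 22.0% | 12.0 | 73% |

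With no true effect (36% in both arms), the 45%/18% pattern in both arms gives no spurious difference. In one arm only, it gives 7.0 points (f = 0.83) or 4.0 points (f = 0.50), in favour of whichever arm loses its attempters.

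**3. Why counting known events is not enough.** Suppose 3-month attempts are kept as events, everyone attends month 3, and event-free dropouts stay missing. The rate is then [a + r(p − a)] / [a + r(1 − a)], where r is retention among those without a 3-month attempt. With f = 0.83:
- 45%/18% in controls only: 39.9% vs 26.5%, a 13.5-point difference.
- Dropout a flat 25%, unrelated to outcome: 41.8% vs 26.5%, a 15.3-point difference, so bias appears where there was none.

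**4. Ideation.** Assumed: SD 7.7 (the pilot's 3-month value); correlations 0.3 (baseline to month 3), 0.2 (baseline to month 6) and 0.6 (month 3 to month 6); true effect 0.34 × 7.7 = 2.62. Control dropout has logit −1.25 + 1.0 × standardized 3-month score; PREVAIL dropout is 25% at random. By simulation:

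| Analysis | Mean estimate (true −2.62) | Rejection with no effect |
|---|---|---|
| Observed data at month 6 | about −1.6 | about 24% |
| Longitudinal, random intercepts (as planned) | −2.1 to −2.2 | 9% to 13% |
| Longitudinal, unstructured covariance | −2.6 | about 5% |

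The ranges cover separate implementations. A random intercept forces one correlation on all pairs of visits, so it understates the link between months 3 and 6 and corrects only part of the bias.

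**5. Dropout depending on the unseen outcome.** If completers show exactly 36% vs 22% and control dropouts also run at 36%, the all-randomized PREVAIL rate is 0.75 × 0.22 + 0.25r, where r is now the attempt rate among PREVAIL dropouts. Significance with 245 per arm is lost at about r = 45% (27.75% vs 36%, z = 1.96). The difference is zero at r = (0.36 − 0.165)/0.25 = 78%. The plan has no analysis of this kind.

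**The case against.** The plan does not ignore missing data. It adjusts for baseline predictors of missingness, fits mixed models that are valid under missing at random if correctly specified, and prespecifies chained-equation imputation. The mixed models appear under the Primary Outcome heading and carry no secondary label; only the imputation does. The missing-data section says initial rather than primary, and the cohort clause speaks of leaving the intervention, not of missed assessments. Separate blinded staff do follow-up, reminders apply to participants generally, and outcomes are sought after withdrawal. All of this stands and limits the point. It does not change which model is the primary test, and the count of 368 and the secondary status of imputation support reading initial as primary.

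Three stronger readings are tempting and should not be drawn:

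- **That known 3-month attempters are discarded.** No section says so. The 6-month time frame equally allows their report to count. The fault is a missing rule.
- **That about four fifths of events are known by month 3.** This divides a small pilot's rate by a planning average from different sources; anything from about one half upward is compatible.
- **That the effect would be halved.** The 7-point figure needs strong dropout after attempts in controls only, which the documents do not support. Mentor contact is planned for 3 months, with at most three optional telephone sessions over the following four weeks, so a large arm difference in month-6 attendance is not established.

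**Conclusion.** The concern holds in limited form and should be fixed. The primary tests rest on the roughly 75% with 6-month data and on baseline adjustment, while the 3-month information that could correct for dropout sits outside them. For attempts, 14 points becomes about 12 to 13 under the assumed strong pattern in both arms, and about 7 to 10 if it applies in controls only. These figures assume that 83% to 50% of events fall by month 3. With dropout unrelated to outcome there is no bias, only lost precision. For ideation, the illustrated loss is about 1 point of 2.62, under assumed correlations and a controls-only pattern.

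A reader might infer that the trial is underpowered or that its primary result will be wrong. Neither follows: the stated power reproduces, 25% is a planning figure consistent with 80% pilot completion at 6 months, and whether bias arises depends on dropout behaviour that the documents do not describe.

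**What to change.** Amend Bivariate/Multivariate Analyses and Approach to Missing Data before outcomes are compared by arm.

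- **(a) Ideation.** Make the primary test the 6-month arm contrast from a longitudinal model of baseline, 3- and 6-month BSS in all randomized participants with any data. Use time as a category, arm-by-time terms, and an unstructured covariance in place of random intercepts only.
- **(b) Attempts.** Define the outcome as any attempt in months 0–3 or 3–6, so that a reported 3-month attempt is an event whether or not month 6 is attended. Make the planned chained-equation imputation primary. Run it within arm with 3-month attempt status and BSS as predictors, impute the missing interval indicators, and then derive the 6-month outcome. Do not merely count known events, because event-free dropouts would stay missing.
- **(c) Sensitivity.** Keep both observed-data regressions as sensitivity analyses and add one delta-adjusted, missing-not-at-random run.

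The cost is SAP wording and modest programming, with no new data. The downside is that the primary results then rest on a likelihood or imputation model rather than a simple regression.
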